4.1.3. Maintenance Study (Phase 3 Maintenance Study)

The study population for the Phase 3 Maintenance Study will be clinical responders from Induction Study 1 or Induction Study 2. The following populations will be rerandomized in a 1:1:1 ratio to guselkumab 200 mg SC q4w, guselkumab 100 mg SC q8w, or placebo SC:

- Guselkumab clinical responders at Week I-12.
- Placebo crossover responders at Week I-24.

Participants will be allocated to an intervention group using permuted block randomization stratified by clinical remission status at maintenance baseline (Yes/No), concomitant use of corticosteroids at maintenance baseline (Yes/No), and induction treatment (guselkumab 400 mg, guselkumab 200 mg, placebo crossover [guselkumab 200 mg], and placebo crossover [guselkumab 400 mg, if chosen as the Phase 3 guselkumab induction dose]). The primary analysis population of the Maintenance Study will comprise randomized and treated participants who have a modified Mayo score of 5 to 9 at induction baseline. In addition to the aforementioned randomized population, guselkumab 24-Week responders and induction placebo responders at Week I-12 from Induction Study 1 or Induction Study 2 will enter the Maintenance Study but will not be rerandomized.

[figure not shown]
Treatment assignments for these groups are shown in the study schema (Figure 4). Placebo SC q8w will be given to the guselkumab 100 mg SC q8w group starting at Week M-0 to maintain the blind throughout the duration of the Maintenance Study. Further information on study intervention administration for the Maintenance Study is provided in Section 6.1.3.

Participants meeting criteria for loss of clinical response (ie, no longer satisfies the definition of clinical response as previously defined in Section 3) during the Maintenance Study will be eligible for a single blinded dose adjustment as described in Section 6.6.1. For additional details on the management of clinical flare and loss of clinical response see Section 4.1.3.1.

For participants who are receiving oral corticosteroids on entry in the Maintenance Study, the investigator must begin tapering the daily dose of corticosteroids at Week M-0 (Section 6.5.1). Other UC-specific medical therapies (ie, oral 5-ASA compounds, 6-MP, AZA, or MTX) must be maintained at stable doses through Week M-44 unless investigator judgment requires that the therapy be discontinued, or the dose reduced because of toxicity or medical necessity (Section 6.5).

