6. STUDY INTERVENTION

6.1. Study Interventions Administered

Intravenous study intervention (including the flush) should be administered over a period of no less than 1 hour, and not more than 2 hours. The infusion (including the flush) should be completed within 6 hours of preparation.

For visits with both IV and SC dosing during Induction Study 1 or Induction Study 2, the IV study intervention should be administered first. The SC study intervention should be administered approximately 30 minutes after the IV study intervention infusion is complete.

During the Maintenance Study, each group will receive 2 SC injections at each visit. The guselkumab 200 mg SC q4w group will receive 2 injections of 100 mg guselkumab at each visit. The guselkumab 100 mg SC q8w group will receive 1 injection of 100 mg guselkumab and 1 injection of placebo to maintain the blind beginning at Week M-4 and 2 SC injections of placebo at alternate visits. The placebo group will receive 2 SC injections of placebo at each visit. Since multiple SC injections are administered at each visit, each injection of study intervention should be given at a different location of the body.

Study intervention administration must be captured in the source documents and the electronic case report form (eCRF). Study-site personnel will instruct participants on how to store and record study intervention for at-home use as indicated for this protocol.

Guselkumab and placebo for guselkumab are Investigational Medicinal Products (IMPs) and will be manufactured and provided under the responsibility of the sponsor. Refer to the guselkumab IB for a list of excipients.

Detailed instructions on the administration of study intervention will be provided in the Site Investigational Product Procedures Manual (IPPM) and Investigational Product Preparation Instructions (IPPI). Of note, instructions on the administration of study intervention in Induction Study 2 will be finalized and provided to investigative sites when the induction dose decision is made and implemented.

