6.1.3. Maintenance Study (Phase 3 Maintenance Study)

In the Maintenance Study, the randomized population will include guselkumab clinical responders at Week I-12 and placebo crossover responders at Week I-24 (from Induction Study 1 or Induction Study 2). These participants will be rerandomized to 1 of 3 study intervention groups as described below.

- **Guselkumab 200 mg SC q4w:** Participants will receive guselkumab 200 mg SC q4w starting at Week M-0 through Week M-44.
- **Guselkumab 100 mg SC q8w:** Participants will receive guselkumab 100 mg SC q8w starting at Week M-4 through Week M-44. Placebo SC will also be administered at alternate visits to maintain the blind.
- **Placebo:** Participants will receive placebo SC q4w starting at Week M-0 through Week M-44.

Participants will remain on their assigned study intervention through Week M-44. Participants who subsequently meet criteria for loss of clinical response will be eligible for a single blinded dose adjustment as described in Section 6.6.1. The primary analysis population for the Maintenance Study will be randomized participants with a modified Mayo score of 5 to 9 at induction baseline.

In the Maintenance Study, the nonrandomized population will consist of guselkumab 24-Week responders and induction placebo responders at Week I-12. Guselkumab 24-Week responders will receive guselkumab 200 mg SC q4w starting at Week M-0 through Week M-44. Induction placebo responders at Week I-12 will receive placebo SC q4w starting at Week M-0 through Week M-44. These populations are not eligible for dose adjustment.

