Efficacy All Nonrandomized and Treated Analysis Set	Includes all the participants (regardless of modified Mayo score) who enter this Maintenance Study but are not randomized (i.e., Guselkumab 24-week clinical responders, and Placebo responders at Week I-12 from Induction Study 1 or Induction Study 2) and receive at least 1 (partial or complete) dose of study intervention in this Maintenance Study.	
Dose Adjustment Analysis Set	Includes all the participants in the Randomized Full Analysis Set who had a dose adjustment.	
Safety Analysis Sets : In general, part intervention assigned.	icipants in each safety analysis set will be analyzed according to the study	
Safety Analysis Set	Includes all participants with a modified Mayo score of 5 to 9 who receive at least 1 (partial or complete) dose of study intervention in this Maintenance Study, including both randomized and nonrandomized.	
Randomized Safety Analysis Set	Includes all participants with a modified Mayo score of 5 to 9 who are randomized in this Maintenance Study (i.e., Guselkumab clinical responders at Week I-12 and Placebo crossover responders at Week I-24 in an Induction Study) and receive at least 1 (partial or complete) dose of study intervention in this Maintenance Study.	
Nonrandomized Safety Analysis Set	Includes all participants with a modified Mayo score of 5 to 9 who enter this Maintenance Study but are not randomized (i.e., Guselkumab 24-week clinical responders, and Placebo responders at Week I-12 from Induction Study 1 or Induction Study 2) and receive at least 1 (partial or complete) dose of study intervention in this Maintenance Study.	
All Treated Analysis Set	Includes all participants (regardless of modified Mayo score) who receive at least 1 (partial or complete) dose of study intervention in this Maintenance Study, including both randomized and nonrandomized.	
Safety All Randomized and Treated Analysis Set	Includes all participants (regardless of modified Mayo score) who are randomized (i.e., Guselkumab clinical responders at Week I-12 and Placebo crossover responders at Week I-24 in an Induction Study) in this Maintenance Study and receive at least 1 (partial or complete) dose of study intervention in this Maintenance Study.	

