5.9. Safety Analyses

Safety data, including but not limited to, AEs and changes in laboratory assessments, will be summarized. Treatment-emergent AEs will be summarized by treatment group and Medical Dictionary for Regulatory Activities (MedDRA) system organ class and preferred terms.

Unless otherwise mentioned, safety summaries will be provided for the **Randomized Safety Analysis Set**, the **Nonrandomized Safety Analysis Set**, and the **Safety Analysis Set**. In general, participants will be analyzed according to their assigned treatment. However, participants assigned to placebo who incorrectly received guselkumab at any time during the maintenance phase (i.e., up to Week M-44) will be analyzed in the guselkumab group; participants assigned to guselkumab who received **only** placebo during the maintenance phase (i.e., up to Week M-44) will be analyzed in the placebo group.

For all continuous safety variables, descriptive statistics by treatment group will include the N, mean, standard deviation, median, minimum, and maximum. Categorical variables will be summarized by treatment group using frequency counts and percentages.

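### The SAP 5.9 safety rule counts correctly dosed 100 mg q8w participants who stop between Week M-0 and the Week M-4 dose under placebo

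*SAP*

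**What the plan says.** SAP 5.9 starts from assigned treatment and then makes two exceptions.

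- Placebo to guselkumab: this covers "participants assigned to placebo who incorrectly received guselkumab at any time during the maintenance phase". The exception applies only to receipt in error.
- Guselkumab to placebo: those assigned to guselkumab who received only "placebo during the maintenance phase (i.e., up to Week M-44) will be analyzed in the placebo group". No error condition is attached.

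The dosing schedule for the 100 mg q8w arm is in the protocol.

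- Protocol 4.1.3: "Placebo SC q8w will be given to the guselkumab 100 mg SC q8w group starting at Week M-0 to maintain the blind".
- Protocol 6.1.3: "Participants will receive guselkumab 100 mg SC q8w starting at Week M-4 through Week M-44".
- Protocol 6.1: this arm has "2 SC injections of placebo at alternate visits".

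For the high-dose arm, Protocol 6.1.3 says: "Participants will receive guselkumab 200 mg SC q4w starting at Week M-0 through Week M-44".

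The Randomized Safety Analysis Set in SAP 4 requires that participants "receive at least 1 (partial or complete) dose of study intervention in this Maintenance Study", so the M-0 placebo injection alone is enough to enter. SAP 5.9.2 counts adverse events as treatment-emergent from that first maintenance administration. We found nothing in either document that exempts the q8w arm from the second exception.

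**The concern.** The planned M-0 placebo is part of the q8w regimen, not a departure from it. Under the rule as written, however, it makes a correctly dosed participant who has not yet reached M-4 look like someone who was given the wrong treatment.

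Whether such a participant is moved depends on what happens next. Take two q8w participants with the same adverse event at week 2, both of whom have so far had only placebo in maintenance. The one who goes on to the M-4 dose is tabulated under 100 mg q8w. The one who stops is tabulated under placebo. The sorting variable is a post-randomization outcome, and discontinuation for an adverse event is itself one of the tabulated safety categories (SAP 5.9.2).

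At stake is the descriptive safety comparison of 100 mg q8w with placebo, and of the two guselkumab doses with each other. Early discontinuations and the events that go with them leave one active column and enter the control column. The other active column has no matching loss.

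**Working it through.** The plan states no figure on this point, so there is none to reproduce. The check sets the rule against the schedule and then sizes the effect under stated assumptions.

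**Step 1: who meets the rule without a dosing error**

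| Assigned arm | Planned M-0 dose | First planned guselkumab | Stops after M-0, before M-4 |
|---|---|---|---|
| 200 mg q4w | guselkumab | M-0 | has had guselkumab; stays |
| 100 mg q8w | placebo | M-4 | has had only placebo; moved to placebo |
| Placebo | placebo | none | stays |

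Dose adjustment does not change this, because Protocol 6.6.1 allows it no earlier than Week M-8.

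**Step 2: how many move**

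Inputs: the planned arm size is 161 (Protocol 9.2.3, Table 9). The share d of the q8w arm stopping after M-0 and before the M-4 dose is not in the documents, so a range of 0.5% to 5% is assumed.

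Expected number moved = 161 × d. Chance that at least one moves = 1 − (1 − d)^161.

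| d (assumed) | Expected number moved | Chance of at least one |
|---|---|---|
| 0.5% | 0.8 | 55% |
| 1% | 1.6 | 80% |
| 2% | 3.2 | 96% |
| 3% | 4.8 | 99% |
| 5% | 8.1 | >99% |

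**Step 3: what a move does to a table through M-44**

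For illustration, assume 8/161 (5.0%) discontinue for an adverse event by M-44 in each of the q8w and placebo arms. Let k of the q8w cases fall before the M-4 dose. The q8w column becomes (8 − k)/(161 − k) and the placebo column (8 + k)/(161 + k).

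| k | 100 mg q8w | Placebo |
|---|---|---|
| 0 | 8/161 = 5.0% | 8/161 = 5.0% |
| 1 | 7/160 = 4.4% | 9/162 = 5.6% |
| 2 | 6/159 = 3.8% | 10/163 = 6.1% |
| 3 | 5/158 = 3.2% | 11/164 = 6.7% |
| 5 | 3/156 = 1.9% | 13/166 = 7.8% |

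One moved case shifts each column by about 0.6 percentage points, in opposite directions. A participant moved without the event changes almost nothing: q8w becomes 8/160 = 5.0% and placebo 8/162 = 4.9%.

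**Step 4: other parts of the plan**

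Efficacy sets are analysed as randomized or assigned (SAP 4) and PK as assigned (SAP 5.10.1.1). Disposition, with reasons for stopping, is by treatment group with no reassignment rule (SAP 5.2). Protocol 9.4.3 summarizes adverse events by intervention group and contains no such rule either. One person could therefore appear as a q8w discontinuation in the disposition table and as a placebo discontinuation in the adverse event table.

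**The case against.** The best defence is that classifying safety by treatment received is legitimate. A q8w participant who stops before M-4 has had induction guselkumab and then placebo, the same maintenance exposure as the placebo arm, and counting their events under 100 mg attributes them to a dose never given. That would carry weight if the rule classified by exposure at the time of the event. It does not: the participant who continues keeps the same placebo-period event in the q8w column.

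A second defence is that both exceptions were probably meant for dosing errors. The word restricting the first is needed there anyway, because placebo participants can properly receive guselkumab through dose adjustment (Protocol 6.6.1). Its absence from the second therefore proves nothing about intent. This is fair, but a programmer following the text would still move these participants.

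Three points on size stand. Safety is descriptive, so no test or error rate is affected. Discontinuations also appear in the disposition tables and in individual listings (SAP 5.2, 5.9.2). And the larger values of k are high for people who have just responded to induction: 3 stops per 161 in four weeks, if sustained over the eleven four-week intervals to M-44, would imply 1 − (1 − 3/161)^11 ≈ 19% discontinuing for an adverse event.

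A reader might also infer more than the documents support:

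- That the q8w table would show no adverse event discontinuations at all. The tables run through M-44, so later events remain in the q8w column. Only those before the M-4 dose leave it.
- That a withheld M-4 dose stretches the placebo-only window to 12 weeks. No make-up rule is stated, visits have a ±10-day window (Protocol Table 2), dose adjustment can bring guselkumab from M-8, and anyone who later receives guselkumab is not moved.
- That people who leave this early usually leave because of an adverse event. The documents give no such information, and withdrawal of consent and loss to follow-up are also listed exits (Protocol 7.2).

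**Conclusion.** The concern holds as a defect in a stated rule. Applied literally, SAP 5.9 removes correctly dosed 100 mg q8w participants who stop between the M-0 injection and the M-4 dose from their own column and adds them to placebo. The shift has one direction and touches one active arm.

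The effect is probably small. The range of about 1 to 8 participants rests on the planned 161 per arm and an assumed early-stopping share of 0.5% to 5%. The shift of about 0.6 percentage points per moved case also rests on the assumed 8/161 base. If nobody stops in that window, the rule does no harm. It matters most for categories with few events, where one or two cases change the impression given by the table.

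**What to change.** Reword the second exception in SAP 5.9 so that it covers only participants assigned to guselkumab who, because of a dosing error, received only placebo at visits where guselkumab was scheduled. Add that 100 mg q8w participants who stop before their first scheduled guselkumab dose are analysed in the 100 mg q8w group.

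With that change no one moves because of the planned M-0 placebo, and apart from true dosing errors both columns keep their assigned participants. The cost is one or two sentences in the SAP and the matching programming rule before the Week M-44 database lock. No new data are needed.

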5.9.1. Extent of Exposure

The number and percentage of participants who receive study intervention through M-44 will be summarized based on the **Enrolled Analysis Set**. The number of administrations of study intervention received, the cumulative dose of study intervention, and the average duration of follow-up in weeks will be summarized by treatment group through M-44 based on **Randomized Safety Analysis Set**, the **Nonrandomized Safety Analysis Set**, and the **Safety Analysis Set**.

The distribution of participants by study intervention lot through Week M-44 will also be provided based on the **All Treated Analysis Set**.

5.9.2. Adverse Events

The verbatim terms used in the CRF by investigators to identify adverse events will be coded using the Medical Dictionary for Regulatory Activities (MedDRA). Any AE occurring at or after the initial administration of study intervention of this maintenance study is considered to be treatment emergent. All reported treatment-emergent adverse events will be included in the analysis. For each adverse event, the number and percentage of participants who experience at least 1 occurrence of the given event will be summarized by treatment group. Since safety should be assessed relative to exposure and follow-up, all AE summary tables will summarize the average weeks of follow-up and average exposure (number of administrations) for each treatment group.

Type of AEs to assess the safety of participants:

Summary tables will be provided for the following treatment-emergent adverse events (TEAEs):

- AEs (including infections)
- SAEs (SAEs including serious infections)
- Reasonably related AEs as assessed by the investigator

- AEs of severe intensity
- AEs leading to discontinuation of study intervention
- Injection-site reactions

Overall TEAE summary table and number of TEAEs per hundred subject-years of follow-up through Week M-44 for the events above (except for injection-site reactions) will also be provided.

An overall TEAE summary table of events through Week M-44 and frequency and type of AEs will also be provided for the All Treated Analysis Set, Safety All Randomized and Treated Analysis Set, and Safety All Nonrandomized and Treated Analysis Set.

In addition to the summary tables, listings will be provided for participants in the **All Treated Analysis Set** who:

- Had SAEs
- Had AEs of severe intensity
- Had AEs leading to discontinuation of study intervention
- Died
- AE of special interest (malignancy and tuberculosis)
- Other AEs of interest (e.g., opportunistic infections, MACE [CV death, nonfatal MI, nonfatal stroke], drug-related hepatic disorders, venous thromboembolism (VTE), anaphylactic reactions, and serum-sickness)

The above AEs will either be presented in a listing or described in the clinical study report. A list of AEs of special interest and other AEs of interest are provided in Appendix 7.

Definitions

- A reasonably related AE is defined as any event with a relationship to study agent of 'Very likely', 'Probable', or 'Possible' on the AE eCRF page or if the relationship to study agent is missing.
- An infection is any AE that was recorded based on the MedDRA system organ class "Infections and Infestations".
- A study intervention injection-site reaction is any reaction at an SC study intervention injection site that was recorded as an injection-site reaction by the investigator on the eCRF.

5.9.3. Additional Safety Assessments

5.9.3.1. Clinical Laboratory Tests

Laboratory assessments include, but are not limited to, the assessments listed below:

• Hematology: hemoglobin, hematocrit, platelet count, total and differential WBC count.

• Blood chemistry: total and direct bilirubin, alanine aminotransferase (ALT), aspartate aminotransferase (AST), alkaline phosphatase, albumin, total protein, calcium, phosphate, sodium, potassium, chloride, blood urea nitrogen (BUN), and creatinine.

The maintenance baseline value for a participant is the value closest to but prior to the first dose of study agent of the maintenance study unless specified otherwise. In addition, change from maintenance baseline is defined to be the assessment at the post-maintenance baseline visit minus the assessment at maintenance baseline. There will be no imputation for missing laboratory values.

Laboratory parameters and change from maintenance baseline in laboratory parameters (hematology and chemistry) through Week M-44 will be summarized and displayed by treatment group based on the **Randomized Safety Analysis Set** and **the Nonrandomized Safety Analysis Set**.

The following summaries will also be presented through Week M-44 for the **Randomized Safety Analysis Set**, the **Nonrandomized Safety Analysis Set**, and the **Safety Analysis Set**:

- Summary of maximum modified National Cancer Institute Common Terminology Criteria for Adverse Events (NCI-CTCAE) toxicity grade for post-maintenance baseline laboratory values through Week M-44 for the predefined hematology and chemistry lab parameters except for liver tests (i.e., ALT, AST, alkaline phosphatase, and total bilirubin). This summary will also be presented for the **All Treated Analysis Set**. Shift tables for maximum modified NCI-CTCAE toxicity grade from maintenance baseline through Week M-44 will be summarized for the predefined hematology and chemistry lab parameters except for liver tests (i.e., ALT, AST, alkaline phosphatase, and total bilirubin).
- Summary of maximum post-maintenance baseline measurement through Week M-44 for liver tests (i.e., ALT, AST, alkaline phosphatase, and total bilirubin) relative to ULN threshold. This summary will also be presented for the All Treated Analysis Set, the Safety All Randomized, the Treated Analysis Set, and the Safety All Nonrandomized and Treated Analysis Set.

Line graphs will also be provided for ALT, AST, total bilirubin, and alkaline phosphatase.

Select clinical laboratory test analyses will utilize a modified NCI-CTCAE toxicity grade (Appendix 9), and liver tests (i.e., ALT, AST, total bilirubin, and alkaline phosphatase) will use the predefined upper limit normal (ULN) thresholds (Appendix 10).

Listings based on the **All Treated Analysis Set** will be provided for participants with any of the following:

• Abnormal post-maintenance baseline laboratory values of toxicity grade ≥ 2 except liver tests

- Statistical Analysis Plan CNTO1959UCO3001 Amendment 2
- Post-maintenance baseline elevated liver tests of AST or ALT \geq 5xULN, or total bilirubin \geq 2xULN, or alkaline phosphatase \geq 2xULN
- Post-maintenance baseline elevated liver tests with combined ALT or $AST \ge 3xULN$ and total bilirubin $\ge 2xULN$.

